As several different medications are utilized within this study, it is important to monitor side effects of the medications, and see if these profiles change under the conditions of the study. We will collect data on the incidence and severity of opioid central and/or systemic side effects – pruritus, nausea/vomiting (not associated with hypotension), somnolence, and respiratory depression. Somnolence will be graded using a published perioperative somnolence scale (23). Measurements of nausea/vomiting and pruritus will make use of previously published scales (24). Respiratory depression will be considered to be present if the respiratory rate is < 10 breaths/min. We will also make note of both the type and amount of treatment given for these opioid-related side-effects. In addition, we will collect data on the incidence and severity of ropivacaine systemic side effects – tinnitus, perioral numbness, metallic taste, and seizures – and will characterize both the type and amount of treatment required.

Breast-feeding success and safety will be monitored during this study. Breast feeding success will be measured using LATCH Scores (25) obtained in the PACU, and once per shift on the mother-baby unit for 72 hours. These will be assigned by either the labor and delivery nurses or by the nurses in the post-partum ward. We will also assess the proportion of mothers breast-feeding their infants at 24, 48, 72hr, and during their 4-6 week and 3 month follow-up phone calls. Maternal plasma and breast milk concentrations have been measured during epidural analgesia with ropivacaine (0.125%)

for labor, with the breast milk-plasma ratio being somewhere between 0.23 and 0.25 at 18-24hr (26). Surprisingly, the literature is silent regarding the concentration of ropivacaine in human breast milk after continuous wound infusion.

Both the cesarean section incision and the catheter insertion site will be evaluated. Any catheter- or infiltrate-related issues like wound infection and seroma formation will be noted. Wounds will be assessed for infection or dehiscence at 24, 48, and 72hr. At the 4-6 week and 3-month follow-up phone calls the patient will be asked about the presence of wound dysesthesia (numbness, tingling, burning, pricking, allodynia, or hyperesthesia). The patient will also be asked about the occurrence of infection, dehiscence, and keloid formation at this time.

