# **Statistical Analysis**

Based on a preliminary sample size calculation using an  $\alpha$  risk of 0.05, a  $\beta$  risk of 0.2, and an effect size involving a 40% reduction in pain scores, we estimate that 20 patients are needed in each arm of the study. Data normality will be tested using the Kolmorgorov-Smirnov test. Normally distributed data will be presented as means  $\pm$  SD, whereas non-normally distributed data will be expressed as medians with interquartile ranges. Categorical data will be reported as frequencies. VAS scores will be analyzed using two-way ANOVA for repeated measures. Non-normal data will be analyzed using the Friedman test. Categorical data will be analyzed using the X test. Multiple comparisons will use a Bonferroni correction. Differences will be considered statistically significant at a P<0.05.

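### No named test uses the order of the side-effect grades to compare the three arms; naming a rank test for graded severity is a free improvement

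*Combined protocol and SAP*

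**What the plan says.** The Objectives section lists among the secondary outcomes the "incidence and severity of opioid central and/or systemic side effects". The effects are pruritus, nausea/vomiting, somnolence and respiratory depression. "Somnolence will be graded using a published perioperative somnolence scale", and nausea/vomiting and pruritus are measured on other published scales. The number of grades, the expected distribution and the assessment times are not given for any of the three. Respiratory depression is different: it is a yes/no outcome defined by a respiratory-rate threshold.

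The Statistical Analysis section names three tests:
- two-way repeated-measures ANOVA, for the VAS scores;
- Friedman: "Non-normal data will be analyzed using the Friedman test";
- X²: "Categorical data will be analyzed using the" X² test.

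It adds a Bonferroni correction for multiple comparisons, without a count of comparisons, and a 0.05 significance level. It does not say whether a severity grade counts as categorical or as non-normal data.

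**The concern.** Severity grades are ordered, and the question is whether they shift between three independent groups of 20. Neither test that could apply answers that question well.

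Pearson X² gives the same result if the grade labels are shuffled, so a move from severe to mild counts like any other change of category. It also spreads its sensitivity over (arms − 1) × (grades − 1) degrees of freedom, while a rank comparison of three arms uses 2. Friedman compares repeated conditions within the same subjects and is not a test between independent arms.

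The stake is efficiency on a secondary outcome. With 20 women per arm, a null X² result on severity could be read as no effect when an order-using test on the same scores had a better chance of showing one. Leaving the test unnamed also means that it would be chosen with the data in hand.

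**Working it through.** **Plan's own figure.** The only stated calculation is 20 per arm for a 40% reduction in pain scores (α 0.05, β 0.2). No SD or control mean is given, so it can only be solved backwards: 20 per arm needs a standardised difference of 0.886 (two-sided), that is an SD of 0.40/0.886 = 45% of the control mean. No power is stated for side-effect severity, so there is nothing to reproduce for this outcome.

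**Inputs from the documents.** Three arms, 20 women each, α = 0.05 (two-sided assumed).

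**Assumed inputs.** Number of grades, saline distribution and effect size. Effects are cumulative odds ratios (OR) for a milder grade: cumulative odds in a ropivacaine arm = OR × cumulative odds on saline.

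Example with saline 30/30/25/15% and OR 4:
- lowest grade: odds 0.30/0.70 = 0.429; ×4 = 1.714; probability 0.632
- lowest two grades: 0.60/0.40 = 1.5; ×4 = 6; probability 0.857
- lowest three grades: 0.85/0.15 = 5.67; ×4 = 22.7; probability 0.958
- resulting split: about 63/23/10/4%

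**Degrees of freedom.** X² with four grades: (3 − 1)(4 − 1) = 6; with three grades: (3 − 1)(3 − 1) = 4. Kruskal-Wallis: 3 − 1 = 2.

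**Simulated power, 3 × 20 women.** Relative loss = 1 − (X² power)/(Kruskal-Wallis power).

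| Saline grades | OR at 0.1%, 0.2% | X² | Kruskal-Wallis | Relative loss |
|---|---|---|---|---|
| 30/30/25/15% | 2, 4 | 33% | 51% | 1 − 33/51 = 35% |
| 30/30/25/15% | 3, 3 | 29% | 46% | 1 − 29/46 = 37% |
| 30/30/25/15% | 4, 4 | 46% | 67% | 1 − 46/67 = 31% |
| 40/40/20% | 2, 4 | 37% | 47% | 1 − 37/47 = 21% |
| 40/40/20% | 3, 3 | 33% | 44% | 1 − 33/44 = 25% |
| 40/40/20% | 4, 4 | 48% | 61% | 1 − 48/61 = 21% |
| four grades, 70% at lowest | 2, 4 | 13% | 27% | about 50% |

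With no effect, both tests reject in about 5% of trials under the 30/30/25/15% split, so the gain is not bought with type I error.

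**How the loss varies.** With four evenly spread grades and an effect rising with dose, the loss falls from 37% at OR 3 to 35% (OR 4), 26% (OR 6) and 16% (OR 10). Over OR 2 to 20 and three to five grades it runs from about 1% to 53%. For yes/no outcomes it is essentially nil. In an assumed case where the spread changes but the level does not, X² has 86% power against 6% for Kruskal-Wallis.

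**Pairwise comparisons.** For 20 against 20, four even grades, OR 4 and α = 0.025 (0.05 over two comparisons with saline): X² 34%, Wilcoxon rank-sum 53%.

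**Sparse cells.** With equal arms, an expected count is 20 × (women with that grade)/60, or one third of that total. It falls below 5 whenever fewer than 15 of the 60 women have the grade. In the four-grade scenarios about 45–75% of cells were below 5, so the X² approximation is also weak.

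**The case against.** The strongest reply has five parts.

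1. *The plan does not assign severity to X².* This stands. A reader might infer that the plan chose X² for these grades, but the Statistical Analysis section never classifies them and its Friedman sentence could equally apply. The point survives because that reading also leaves no suitable between-arm test.

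2. *The loss has no anchor in the documents.* This also stands. A reader might take about a third of the power as a fixed cost; that figure belongs to one assumed four-grade split. The proportional-odds shift used here also favours rank tests.

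3. *The plan does not predict milder side effects.* Correct. The Introduction hopes for fewer opioid side effects, and the benefits section speaks of incidence and treatment. Neither mentions severity. Severity is nevertheless an outcome that the Objectives say will be collected.

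4. *X² on incidence recovers much of the gap.* Under the 30/30/25/15% split, any-versus-none has 46%, 39% and 58% power in the three scenarios, against 51%, 46% and 67% for Kruskal-Wallis. With 70% at the lowest grade it does about as well as Kruskal-Wallis. This limits the consequence for shifts of this kind, but it tests whether an effect occurred, not how severe it was.

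5. *The outcome is secondary, with no power claim.* True. The 20 per arm rests on pain scores and is untouched. Nor does it follow that a rank test would find what X² misses: Kruskal-Wallis itself reaches only 44–67% in the three- and four-grade scenarios above, and 27% in the sparse one.

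**Conclusion.** The concern holds in a limited form. Graded severity is a planned outcome, and no test named in the plan uses the order of the grades to compare independent arms. For a consistent shift in severity, X² gives up power relative to Kruskal-Wallis: about 20–25% relative with three grades (40/40/20%), about 30–37% with four grades (30/30/25/15%), and about 50% with 70% of women at the lowest of four grades. The loss is small at very large effects when the grades are well spread, and the ranking reverses if only the spread changes. All these figures rest on assumed scales, distributions and odds ratios.

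The documents do not support reading this as a threat to the primary analysis, to the sample size or to type I error. It is a free improvement to a secondary analysis.

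**What to change.** Add to the Statistical Analysis section:

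> *Graded severity scores (pruritus, nausea/vomiting, somnolence), summarised as the worst grade per woman over 0–72 hr, will be compared between arms with the Kruskal-Wallis test, with Bonferroni-corrected pairwise Wilcoxon rank-sum tests; X² is kept for unordered and yes/no outcomes, including incidence.*

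The same edit should state how many pairwise comparisons the Bonferroni correction covers: 0.05/2 = 0.025 for each dose against saline, or 0.05/3 = 0.0167 for all three pairs. Since no assessment times are given for these scales, it should also say which recorded grades feed the worst grade.

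A dose-trend test is not proposed: if only the low-dose arm differs, it has almost no power (about 4–9%).

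The cost is one sentence. It needs no new data and no extra patients, and it keeps type I error at about 5%.

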### **IRB** Protocol

### Multimodal Post-Cesarean Analgesia with Spinal Morphine and Continuous Wound Infiltration of Ropivacaine Using the OnQ® Elastomeric Pump: A Dose-Ranging Study Using a High-Volume, Low-Dose Protocol PI: [name]

Abstract:

The purpose of the proposed study is aimed to determine whether continuous subfascial infusion of ropivacaine using the On-O® elastomeric pump in combination with intrathecal (IT) preservative-free morphine (PFM) will improve post-operative cesarean section pain relative to IT PFM alone (the current standard of care). Using a doubleblinded, randomized, placebo-controlled study design, 60 women undergoing their first, second or third cesarean section will be randomly assigned to one of 3 different groups receiving either saline (control, n=20) or ropivacaine (0.1% or 0.2%, experimental groups n=20 in each) subfascially via the elastomeric pump. We will enroll up to 70 subjects to achieve 60 randomized and treated subjects, to account for screen failures and/or early terminations, All participants will receive an IT dose of 200mcg of PFM as part of a standardized spinal anesthetic for their operative procedure. During closure of their abdomen, all patients will undergo placement of a multi-orifice, silver-impregnated catheter in the subfascial space. At the conclusion of the surgery, the catheter will be bolused with 8ml of one of the three test solutions, after which an On-O® elastomeric pump (containing the same solution as initially administered through the catheter) will be attached to infuse the test solution at a rate of 8ml/hr. The infusion system will then be left in place for up to 72hr. Adjunctive pain medicines (ketorolac, morphine, ibuprofen, and oxycodone-acetaminophen) will be available for the treatment of breakthrough pain during hospitalization. The primary outcome being measured in the study is postoperative pain with movement as assessed immediately after the study bolus (baseline) and during the immediate post-operative period, when leaving the PACU (2hr), 6hr, 12hr, 24hr, 48hr, and 72hr post-op. Pain will also be evaluated by telephone at 4-6 weeks and 3mo after surgery. A visual acuity pain scale (VAPS) will be used to measure patient pain levels while hospitalized whereas pain at the 4-6 week visit and 3mo will be quantitated using a numeric pain scale (NPS). Secondary outcomes to be studied include degree of pain at rest, time to first rescue medication, time to first opioid use, amount of

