risks of myocardial infarction, aneurysmal rupture, thrombophlebitis, post-operative atelectasis and pneumonia. Poorly controlled post-surgical pain relief also influences the risk of developing chronic post-surgical pain (CPSP) (5, 6). CPSP is defined as pain of at least 2mo duration which develops after a surgical procedure, and which is not related to any other causes of pain (infection, malignancy, etc.) or to pain continuing from a pre-existing pain problem (7). The incidence of CPSP after cesarean section is believed to be between 10-12% (5, 6), meaning that as many as 168,000 women might be affected with this each year. Even more troubling is that an estimated 4% of the women undergoing cesarean section (~48,000) actually develop disabling chronic pain defined as pain > 5 on a scale from 0 to 10 (6). Recognition of the above psychological and physical attributes of pain led to the Joint Commission recommendation to treat pain as the fifth vial sign, with the stated goal for US healthcare facilities to uniformly achieve pain scores  $\leq$  3 out of 10 (8).

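### Chi-square is the only test named for categorical outcomes; at 20 per arm, rare safety events give sparse tables in which its p-value can fall on the other side of 0.05 from the exact one

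*Combined protocol and SAP*

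**What the plan says.** The Statistical Analysis section gives one rule for every categorical outcome: "Categorical data will be analyzed using the X 2 test". The threshold is also general: "Differences will be considered statistically significant at a P<0.05". For multiplicity it says "Multiple comparisons will use a Bonferroni correction" and does not define the family of comparisons. No exact or other small-count test appears anywhere in the document.

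The abstract sets the arms: "saline (control, n=20) or ropivacaine (0.1% or 0.2%, experimental groups n=20 in each".

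The Objectives section lists the categorical outcomes likely to be rare: respiratory depression, tinnitus, perioral numbness, metallic taste, seizures, and wound infection or dehiscence. For the catheter it adds "Any catheter- or infiltrate-related issues like wound infection and seroma formation will be noted". No expected rate is given for any of these. The section on patient safety describes major toxicity as very unlikely and the infection risk as small, again without figures.

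**The concern.** The chi-square p-value is a large-sample approximation. With a handful of events in 60 women it can differ from the exact p-value by a factor of two or more, and the two can fall on opposite sides of 0.05. A reader would then be told that a small cluster of wound or toxicity events in one arm is statistically significant when the exact calculation does not say so.

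The plan also leaves the choice open. An analyst who meets a sparse table may switch to an exact test or stay with chi-square after seeing the counts. A rule written in advance removes that discretion.

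**Working it through.** **Inputs.** 20 women per arm and 60 in total (abstract; Statistical Analysis); threshold 0.05 (Statistical Analysis). The documents give no event rates for the safety outcomes, so true rates of 2-15% are assumed as a range.

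**The plan's own figure.** The only computed figure is the sample size: "we estimate that 20 patients are needed in each arm of the study". It concerns pain scores and cannot be reproduced, because no standard deviation is given. By the usual two-sided formula, n = 20 implies a standardized difference of √(2/20) × (1.960 + 0.842) = 0.886, so a 40% reduction needs an SD of 0.40/0.886, about 45% of the control mean. Only the arm size matters for this point.

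**When tables are sparse.** With T events in three equal arms, the expected count per arm is T/3. This is below 5 whenever T < 15, that is, below 15/60 = 25% overall. For a pair of arms it is T/2, below 5 whenever T < 10.

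**Table 3/0/0, chi-square.** Expected events are 1 per arm and expected non-events 19. The statistic is (3−1)²/1 + 2 × (0−1)²/1 + (17−19)²/19 + 2 × (20−19)²/19 = 6 + 6/19 = 6.316. On 2 degrees of freedom, p = exp(−6.316/2) = 0.0425.

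**Table 3/0/0, exact.** Given three events in total, the chance that all fall in one arm is 3 × C(20,3)/C(60,3) = 3420/34220 = 0.0999. This is also the randomization p-value, if every split of the 60 women into three arms of 20 is equally likely.

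**Other tables (20 per arm):**

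| Events | Chi-square p | Exact p |
|---|---|---|
| 3/0/0 | 0.0425 | 0.0999 |
| 4/0/0 | 0.014 | 0.030 |
| 5/1/0 | 0.020 | 0.039 |
| 5/1/1 | 0.075 | 0.192 |
| 3 v 0 | 0.072 | 0.231 |
| 4 v 0 | 0.035 | 0.106 |
| 6 v 1 | 0.037 | 0.091 |

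The tests disagree at 0.05 for 3/0/0, 4 v 0 and 6 v 1, and agree for the other four.

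**Bonferroni on the pairs.** For two comparisons, 4 v 0 becomes 2 × 0.0350 = 0.070 and 6 v 1 becomes 2 × 0.0375 = 0.075. For three, they become 0.105 and 0.112. If the correction covers the pairs, neither is significant.

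**Size at nominal 5%, three-arm test, full enumeration with a common true rate:**

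| True rate | Chi-square | Fisher-Freeman-Halton |
|---|---|---|
| 2% | 1.0% | 0.08% |
| 5% | 3.2% | 0.9% |
| 10% | 3.9% | 2.3% |
| 15% | 4.5% | 3.0% |

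**How often the example matters.** At a true rate of 5%, exactly three events occur in C(60,3) × 0.05³ × 0.95⁵⁷ = 23% of trials, and all three fall in one arm in 0.23 × 0.0999 = 2.3%.

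**Mid-p.** The three arrangements of 3/0/0 are equally likely and make up the whole exact p-value, so the mid-p is 0.0999/2 = 0.04997, still below 0.05.

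**Zero events.** The exact two-sided 95% upper limit for 0 of 20 is 1 − 0.025^(1/20) = 16.8%.

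**The case against.** The strongest reply is that chi-square does its job on average. Its size stays below 5% at every assumed rate in the table, while the exact test is well below nominal. In a trial of 60 women that costs ability to see a safety signal. This stands. A reader might infer from the 3/0/0 example that chi-square inflates false positives across the trial; the size figures do not support that. Given exactly three events, chi-square does reject 10.0% of the time under the null, but that is one event total, and at other totals it rejects less often.

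It can also be said that the gap depends on conditioning on the event total. Exact p-values that do not fix the total, ordered by chi-square and maximized over common true rates of 0.5-50%, are 0.048 for 3/0/0, 0.039 for 4 v 0 and 0.049 for 6 v 1, on the same side of 0.05 as chi-square. So the choice is partly one of method. Conditioning remains a conventional default for sparse tables, and for 3/0/0 it agrees with the randomization.

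Bonferroni may already remove the pairwise examples. The plan does not say which comparisons it covers, so the three-arm test of a single outcome is the example that holds most clearly. It too would lose significance if the correction were applied across outcomes.

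Finally, a reader might count chronic pain as a sparse categorical outcome, because the background says "The incidence of CPSP after cesarean section is believed to be between 10-12" per cent, or 2.0-2.4 women per arm of 20. The documents do not support that step: the Objectives section measures later pain on a 0-10 numeric scale and defines no yes/no chronic-pain endpoint.

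**Conclusion.** The gap is real and minor. The plan fixes chi-square for all categorical data at an arm size where rare outcomes will often produce expected counts below 5, and for some of those tables the choice of test decides significance. The clearest case is 3/0/0, at 0.0425 against 0.0999. For other sparse tables, such as 4/0/0 and 5/1/0, both tests give the same answer.

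The conclusion assumes that the listed safety outcomes are in fact rare (the documents give no rates), that the three-arm test is judged at an unadjusted 0.05, and that the conditional exact test is the reference. It does not extend to the primary pain-score analysis, to the sample size, or to the commoner categorical outcomes with adequate counts.

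**What to change.** Add one sentence to the Statistical Analysis section: when any expected cell count is below 5, the Fisher-Freeman-Halton exact test replaces chi-square, with Fisher's exact test for comparisons of two arms; chi-square is kept otherwise. Do not offer mid-p as an option, because it leaves the 3/0/0 table just below 0.05. Add that event rates will be reported by arm with exact 95% intervals, so that zero events in 20 is not read as evidence of safety when rates up to 16.8% remain compatible with it.

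The change affects no enrolment, data collection or treatment. Its price is conservatism: the exact test's size is about 0.1-3.0% at true rates of 2-15%, so it has less power for rare-event differences, and with only three events in total it cannot reach 0.05, since 3/0/0 is already the most extreme table. The intervals and raw counts should therefore carry most of the safety interpretation.

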### **Introduction and Background:**

The primary hypothesis of this study is that post-cesarean section pain with movement will be significantly improved in women treated with IT PFM by the addition of continuous subfascial wound infiltration with ropivacaine. There are approximately 4 million deliveries in the United States every year; with about 30% of these deliveries being cesarean sections. This makes cesarean section one of the most common surgeries performed today. Women experience significant post-operative pain after cesarean sections. Cesarean section patients are unique among surgical patients in that they have to immediately care for their newborns after their procedure, and their infants may be affected by systemically-administered maternal pain medications if breastfeeding. Therefore, this population requires the combination of maximal pain relief with minimal sedation, while minimizing the exposure of infants to clinically-significant amounts of drugs in breast milk. This encourages further studies that will elucidate better means of accomplishing ideal post-operative pain.

Pain, both intraoperative and postoperative, has been shown to be the anesthetic outcome of greatest concern to women undergoing cesarean section with the potential side effects of pain relief being of much less concern (1). This was found to be true both in terms of absolute ranking and when using a relative value score. Pain as part of the childbirth experience may predispose the parturient to the development of post-traumatic stress disorder (2). It has also been suggested that pain after cesarean section decreases the effectiveness of breast feeding leading to more formula and pacifier use (3, 4). In addition to the obvious psychological aversion to pain by patients, it is well-known that pain can stimulate a variety of potentially detrimental physiological effects such as tachycardia, hypertension, respiratory splinting, and inactivity, which in turn can lead to

IRB00073292

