To date, long-acting neuraxial opioids like PFM provide the gold standard for postcesarean delivery analgesia whether given via the IT or epidural route, providing excellent pain relief for the first 24hr while allowing the mother to ambulate and care for her child (18, 19). However, it is clear that neuraxial opioids do not provide complete analgesia for cesarean section when used as primary agents, with more than 70% of patients requesting further analgesia (19). Even when codeine with acetaminophen is given prn, 33% of women in one study still experienced inadequate analgesia (18). Pain with movement appears to be the most poorly treated pain phenomenon using neuraxial PFM (19). Again, this points to the importance of multimodal pain control in obstetric patients. Surprisingly, while continuous wound infiltration has been examined as a primary technique for post-cesarean pain relief (13,14,15,16) and has even been compared for efficacy to epidural (13,14) and IT (17) post-cesarean analgesia, no one has tested to see if continuous wound infiltration with LAs improves the analgesia obtained from IT PFM. However, it is standard practice of some obstetricians in our institution to use the continuous wound infiltration system on every patient undergoing a cesarean section whether they have IT PFM or not. The purpose of the proposed study is to examine the hypothesis that continuous wound infusion with ropivacaine using a highvolume, low-dose protocol will significantly improve pain with movement after cesarean section in patients who have received our standard dose of IT PFM. A control group (IT PFM + saline wound infusion) will be compared to two groups receiving both IT PFM along with one of two doses of ropivacaine (experimental groups) using the OnQ® elastomeric pump for delivery of the infusions. We have purposefully used lower concentrations of ropivacaine (0.1-0.2%) along with higher volumes in recognition that the nerves to be anesthetized are of smaller diameter, and therefore require lower concentrations of LA for this effect; while ensuring a high enough volume to completely

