# **Objectives:**

The primary outcome measured in this study is post-operative pain with movement measured both during cough and 20° straight leg raise. Pain at rest will also be evaluated. All types of pain will be measured using a visual analogue pain scale (VAPS) determined using a 100mm line with the patient making a mark on the line between no pain and worst pain ever (12). Pain scores will be collected after the bolus of study medication/placebo (zero time), at PACU discharge (2hr), 6hr, 12hr, 24hr, 48hr, and 72hr post-cesarean section. Pain at 4-6 weeks and 3mo will be quantitated over the telephone using a numerical pain scale (NPS) with 0 being no pain and 10 being the worst pain imaginable. In addition to the pain scores, pain with movement will be further evaluated qualitatively using the short-form McGill pain questionnaire (22) at all time-points in the study. This will allow us to look at pain quality (sharp, burning, etc.), as well as examining the affective components (exhausting, fearful, etc.) of the pain.

There are several secondary outcomes of this study that can be divided into rescue medication information, medication side effects, breastfeeding, wound evaluation, patient satisfaction, and cost-analysis.

Rescue medication data will be collected during the hospitalization period (0-72hr). We will note the time to dosing with the first rescue medication for breakthrough pain. After the first rescue medication is given, the patients will be eligible for further doses of IV or

PO pain medicines for continued breakthrough pain as needed (see **Study Design and Methods** section below for specifics). The time to first opioid use for pain will also be recorded whether this entails IV or PO administration. Additionally, we will quantitate narcotic use in terms of morphine equivalents given (in mg) both by post-operative day and with a cumulative total. The total dose of NSAIDs (in mg) will be recorded for each of the first three postoperative days, along with a cumulative total. We will also be measuring the proportion of patients who require opioid supplementation at 0, 2, 6, 12, 24, 48, and 72 hours post-op. We will also ask if patients are still requiring opioids and/or NSAIDs for surgical discomfort along with inquiring about the amount of each used per day at the 4-6 week and 3 month follow-up telephone calls.

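### Do two movement manoeuvres, an unlisted Bonferroni family and an undocumented 20 per arm leave the primary analysis in need of change?

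*Combined protocol and SAP*

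**What the plan says.** The Objectives section defines the endpoint: "The primary outcome measured in this study is post-operative pain with movement measured both during cough and 20° straight leg raise". The abstract treats it as a single outcome followed over time: "The primary outcome being measured in the study is postoperative pain with movement as assessed immediately after the study bolus", then at 2, 6, 12, 24, 48 and 72 hours. The hypothesis in the Introduction and Background is also a single claim, that "pain with movement will be significantly improved in women treated with IT PFM by the addition of continuous subfascial wound infiltration". The same section names the comparison: the saline control "will be compared to two groups receiving both IT PFM along with one of two doses of ropivacaine".

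The Statistical Analysis section sets alpha at 0.05, beta at 0.2 and the effect at a 40% reduction in pain scores, and concludes that "we estimate that 20 patients are needed in each arm of the study". It calls this calculation preliminary. For the analysis it says "VAS scores will be analyzed using two-way ANOVA for repeated measures" and "Multiple comparisons will use a Bonferroni correction", with significance at P<0.05.

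**The concern.** Three things are not written down.

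- **The primary result.** Cough and leg raise give two scores. The plan does not say whether they are averaged, whether one leads, or whether both must succeed. It also does not say whether the arm term or the arm-by-time term decides.
- **The Bonferroni family.** The divisor could be 2 (two doses against saline), 3 (all pairs), 4 (two doses by two manoeuvres), 14 (two doses by seven times) or 28 (all three together).
- **The powered comparison.** With no control mean, SD, test or sidedness, the 80% cannot be tied to a particular contrast or to a corrected alpha.

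The stake would be the primary conclusion. Two analysts could read the same data differently, and a free choice between manoeuvres after unblinding would raise the false-positive rate.

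**Working it through.** **Inputs.** From the Statistical Analysis section: alpha 0.05, power 0.80, 40% reduction, 20 per arm. From the abstract: three equal arms and seven in-hospital times. Not given, so assumed: the SD as a fraction of the control mean (CV), the correlation r between manoeuvres, and sidedness.

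**1. Can 20 per arm be reproduced?** For two means, n = 2(z_{1-α/2} + z_{0.80})² × (CV/0.40)². At two-sided 0.05 this is 2(1.960 + 0.842)² × (CV/0.40)² = 15.70 × (CV/0.40)².

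- CV 0.30: 15.70 × 0.5625 = 8.8, so 9 per arm
- CV 0.45: 15.70 × 1.2656 = 19.9, so 20 per arm
- CV 0.60: 15.70 × 2.25 = 35.3, so 36 per arm

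The figure depends wholly on the CV, so it can be neither confirmed nor refuted.

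**2. Which readings fit 20 per arm and 80% power?** I solved for the standardised difference d (noncentral t with 38 df, or noncentral F with 2 and 57 df). Then CV = 0.40/d.

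| Reading | d | CV |
|---|---|---|
| One pairwise test, one-sided 0.05 | 0.801 | 0.500 |
| Global F at 0.05, one or both doses fully effective | 0.873 | 0.458 |
| One pairwise test, two-sided 0.05 | 0.909 | 0.440 |
| Two contrasts at 0.025 | 1.009 | 0.397 |
| Three pairs at 0.0167 | 1.064 | 0.376 |

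All five fit. In the last two the Bonferroni correction is already paid for within 20 per arm.

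**3. False positives from two manoeuvres.** I simulated 60,000 null trials per setting, three arms of 20, with r = 0.5 and 0.9.

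| Rule | r = 0.5 | r = 0.9 |
|---|---|---|
| F test on each manoeuvre at 0.05 | about 9% | about 7% |
| F test on each manoeuvre at 0.025 | under 5% | under 4% |
| Two dose contrasts at 0.025 on each manoeuvre | about 8.5% | about 7% |
| Two dose contrasts at 0.025 on the averaged score | under 5% | under 5% |

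With two doses by two manoeuvres as the family, each test is at 0.05/4 = 0.0125 and the bound is 4 × 0.0125 = 0.05. The excess appears only when Bonferroni is withheld from the manoeuvres, and the plan's sentence contains no such restriction.

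**4. Does the missing SD imply low power for the planned analysis?** Taking the pairwise 0.05 reading (d = 0.909), single-occasion power per dose at 0.025 is 70%. The plan, however, uses repeated measures. Averaging six post-baseline times multiplies the SD by √((1 + 5r)/6), where r is now the correlation between times, assumed equal, with a constant effect:

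- r = 0.5: factor 0.764, power 92%
- r = 0.7: factor 0.866, power 83%
- r = 0.9: factor 0.957, power 75%

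On the one-sided reading (d = 0.801), single-occasion power at two-sided 0.025 is 58%. If the sizing already used a time-averaged SD, the gain from averaging times is absent. Power can therefore fall on either side of 80%, depending on inputs that the plan does not give.

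**The case for a change.** The strongest case for a change is this. If cough is significant and leg raise is not, or one dose gives p = 0.03, the plan does not say whether the trial succeeded, and settling that after unblinding would be outcome selection. The Statistical Analysis section is the only analysis text and points to no further plan. The Data Collection Instrument mentioned under Study Design and Methodology is not available to check. The choice of family also matters for power: from d = 0.909 on a single occasion, it is 70% with a divisor of 2, 60% with 4 and 33% with 28.

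The omissions stand, but the consequences are weaker than they look. The divisor of 28 treats each time as a separate test, whereas the repeated-measures ANOVA puts all in-hospital times in one model. What remains open there is which term decides. The dose-versus-saline comparisons are named in the Introduction and Background. The Bonferroni sentence covers the manoeuvres unless an analyst chooses to exclude them. A null result for one dose can still be read from its confidence interval, whatever the planning power was.

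Averaging the two manoeuvres would also settle the matter, and it can help power: from 70%, it gives 83% at a between-manoeuvre correlation of 0.5 and 73% at 0.9. But a lead manoeuvre, a requirement that both succeed, or Bonferroni across the two would be equally valid. Choosing among them is a trade-off for the sponsor. Making 0.1% against 0.2% secondary is likewise a choice in a study whose title calls it dose-ranging.

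**Conclusion.** The concern does not hold as a fault in the plan. It identifies missing detail: no rule joining the two manoeuvres, no list of Bonferroni comparisons, no deciding model term, and no inputs behind 20 per arm. No stated number or rule is contradicted. The familywise error of about 7% to 9% needs a reading that withholds Bonferroni from the manoeuvres. With the correction applied to them it stays below 5%, for assumed correlations of 0.5 to 0.9. Twenty per arm is consistent with 80% power at 0.025 if the SD is about 0.40 of the control mean, an assumption the documents neither support nor rule out. The power percentages above are illustrations only and should not be read as the trial's power. An analyst can resolve these points within the existing wording in the usual preparation before unblinding, so no amendment is called for.
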